### 3.6.3. Setting:

Subjects will complete pre-screening, consent and data collection in the OB clinics at WHASC and SAMMC. Interventions will be completed via telephone.

### 3.6.4. Date(s):

Participants will be involved in study related activities for twenty-one months from the time of enrollment.

### 3.6.5. Source of Research Material:

Source of Research Material per Participant (Procedures)	# Routine Care	# Research Driven	# Total Procedures
Research Project Medical Clearance	0	1	1
Screening Visit Interview Questions	0	1	1
Weight	12	7	19
Height	0	5	5
Abdominal Circumference	0	3	3
Contact information	0	7	7
Demographics	0	1	1
International Physical Activity Questionnaire	0	5	5
Breastfeeding Questions	0	2	2
EPDS Depression Screener	3	3	6
Military Fitness Test Scores	0	2	2
Program Evaluation	0	2	2
Modified Pregnancy-Unique Quantification of Emesis and Nausea Index	0	2	2
Weight Gain Recommendations	0	1	1

### 3.6.6. Subjects:

Study participants will be female, active duty military personnel stationed at Joint Base San Antonio.

### 3.6.7. Inclusion/Exclusion Criteria:

Inclusion:

- Participants will be female, DoD Tricare beneficiaries (Active Duty military, retirees and dependents) living in the San Antonio, Texas area receiving medical care at Joint Base San Antonio, and at least 18 years old.
- Participants must be less than 12 weeks gestation upon recruitment (based on the date of their last menstrual period and confirmed by first trimester ultrasound at the first prenatal visit).
- Participants must be within the normal, overweight, or obese BMI ranges upon Baseline measurement.
- Participants must plan to live in the San Antonio, Texas area for at least 1.5 years.

Exclusion:

- Participants who have any medical conditions that limit a participant's ability to engage in changes in dietary intake or increases in physical activity, based on the determination of physicians on the study team.
- Participants who have a high-risk pregnancy (i.e., Type I or II diabetes at conception or current multiple gestation), based on the determination of physicians on the study team.
- Participants who smoke at the time of conception (smoking cessation during pregnancy has significant benefits for fetal health, but the quitting process can be associated with weight gain and thus offers potential study confounds)

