#### 3.6.1. Interventions, Observations, or Data Sought:

**Procedure:** Interested individuals will be directed from our recruitment materials (e.g., posters, flyers, business cards, listservs, and electronic media) to visit the study recruitment office (located in the obstetric clinics) to learn more and determine whether they meet the eligibility criteria. If, after learning more about the study, individuals continue to be interested, written informed consent will be obtained and measures will be administered. The potential participant will also be asked to complete a one-week dietary and exercise self-monitoring run-in, turn in a copy of their fitness scores to study staff (if active duty), and receive medical clearance from their obstetrician to participate. (Note: In the unfortunate event that a potential participant miscarries before being randomized, she will have the opportunity to re-screen if she chooses.) Should she continue to be interested, she will return for a Baseline Visit and will be randomized to 1 of 3 conditions: a) GWG-only; b) PPWL-only; or c) GWG+PPWL and oriented to the assigned treatment condition.

**Randomization:** Participants (n=450) will be randomly allocated to 1 of the 3 conditions, using a computer algorithm under the direction of the study biostatistician, [name], with a sequence blocked by screening BMI category (i.e., normal weight, overweight, obese) in order to ensure equal distribution by condition with respect to BMI category. Each condition will have the same number of subjects.

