**Intervention Overview:** The novel stepped-care behavioral GWG and/or PPWL intervention--designed to assist participants meet the Institute of Medicine (IOM)-recommended GWG guidelines and produce PPWL--will be based on the Look AHEAD Intensive Lifestyle Intervention. The Look AHEAD Intensive Lifestyle Intervention methods are consistent with those utilized in previous studies of effective approaches to producing appropriate GWG and PPWL. However, the Look AHEAD approach offers greater structure and support than some of the methods used in previous work. We will also tailor our intervention to the military lifestyle (e.g., managing stressors such as increases in dietary intake, reduced physical activity related to spouse deployment, environmental facilitators such as access to the free fitness centers). We have previously tailored our interventions to the military lifestyle and environment, and our programs have been extremely well received by military personnel.

**GWG Intervention:** The GWG intervention will begin upon randomization to the GWG-only or the GWG+PPWL arm, and continue until the birth of the participant’s child. This intervention will provide individual, telephone-based sessions (20-30 minutes each), as detailed in Table 1, by trained interventionists. The number of possible telephone sessions will depend on the gestational age at randomization and the level of support needed by the participant to meet the IOM guidelines. The intervention will focus on self-monitoring, clear goals (i.e., GWG, caloric intake exercise), and problem solving.

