#### **6.1. Outcome Measures:**

The primary study outcomes will be a comparison of GWG from baseline to the final gestational weight (either week 32 or week 36, depending on the delivery date) as well as a comparison of weight loss from 6-week postpartum to 12-months postpartum for the 3 intervention arms.

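### The primary gestational weight gain outcome covers a window whose length varies with gestational age at Baseline; naming that variable as a covariate for Hypothesis 1 is a free gain in precision

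*Combined protocol and SAP*

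**What the plan says.** - **Eligibility.** Section 3.6.7, and the matching list in section 6 of the opening summary, ties the limit to recruitment: "Participants must be less than 12 weeks gestation upon recruitment". Dating is by last menstrual period, confirmed by first-trimester ultrasound.
- **Between consent and allocation.** Under Procedure in section 3.6.1, "The potential participant will also be asked to complete a one-week dietary and exercise self-monitoring run-in". She also supplies fitness scores if on active duty and obtains her obstetrician's clearance. Then "she will return for a Baseline Visit and will be randomized to 1 of 3 conditions". The supplied text gives no maximum interval and no gestational limit for that visit.
- **Outcome.** Section 6.1 defines the first primary outcome as "a comparison of GWG from baseline to the final gestational weight (either week 32 or week 36, depending on the delivery date". Section 3.6.8 makes week 36 the end point, with week 32 used for women who deliver before week 36.
- **Intervention.** Section 3.6.1 says "The GWG intervention will begin upon randomization to the GWG-only or the GWG+PPWL arm, and continue until the birth of the participant’s child" and acknowledges that "The number of possible telephone sessions will depend on the gestational age at randomization".
- **Allocation and model.** The sequence is blocked on screening BMI category only (section 3.6.1). Section 6.3 adjusts for differences at baseline without listing variables, and says that further adjustment will be considered if imbalance is found. Gestational age at Baseline is not named, and the outcome is not expressed as gain per week.

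**The concern.** The outcome is a weight difference with a fixed end and a moving start. A woman whose Baseline falls later has fewer weeks in which gain is counted, whatever her arm. Two things move the start: how early she is recruited (any time under 12 weeks) and how long the run-in and clearance take (no stated limit).

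The variable that drives this is known before allocation, yet it is neither a blocking factor nor a named covariate. Baseline weight, if that is among the variables section 6.3 has in mind, does not stand in for it. The spread in start times therefore goes into the residual of the Hypothesis 1 model, and whether it is ever removed depends on a discretionary decision taken after arms have been compared. What is at stake is some precision on a primary outcome, and an adjusted analysis that is not fully fixed in advance.

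**Working it through.** The plan has no figure to reproduce. Section 6.2 gives 150 women per group and no alpha, power, effect size or SD. What follows is an illustration.

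**Inputs from the documents.** Limit under 12 weeks at recruitment (3.6.7); run-in of one week (3.6.1); end point week 36 (3.6.8); weight goals from 5 kg (lower limit, obese) to 16 kg (upper limit, normal weight) (3.6.1, GWG weight goals); 150 per arm (6.2).

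**Assumptions.** Gain spread evenly over 40 weeks; outcome SD 4 to 6 kg without the timing component; SD of gestational age at Baseline 1 to 3 weeks; two-sided alpha 0.05; 80% power before the timing component is added.

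**1. Window length** = 36 − gestational age at Baseline.
- Week 8: 36 − 8 = 28 weeks
- Week 12: 24 weeks
- Week 14: 22 weeks
- Week 16: 20 weeks

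A woman recruited just under 12 weeks reaches Baseline at about week 13 at the earliest if the run-in follows consent.

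**2. Shift in one woman's measured gain.**
- Weekly rate: 5/40 = 0.125 kg to 16/40 = 0.4 kg
- Four weeks later: 4 × 0.125 = 0.5 kg to 4 × 0.4 = 1.6 kg

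**3. Added variance** = (rate × SD of gestational age)² / (outcome SD)².
- Smallest: (0.125 × 1)² / 6² = 0.0156/36 = 0.04%
- Middle: (0.4 × 2)² / 5² = 0.64/25 = 2.6%
- Largest: (0.4 × 3)² / 4² = 1.44/16 = 9%

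**4. Power, two arms of 150.** For a difference that would have 80% power, power = Φ[(1.960 + 0.842) × SD/total SD − 1.960].
- Largest case: total SD = √(16 + 1.44) = 4.176; 2.802 × 4/4.176 = 2.684; Φ(0.724) = 76.5%
- Smallest case: 79.98%

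**5. Chance imbalance between two arms** (95% range) = ±1.96 × SD × √(2/150).
- SD 1 week: ±0.23 weeks, about 0.03 kg at 0.125 kg per week
- SD 3 weeks: ±0.68 weeks, about 0.27 kg at 0.4 kg per week

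Step 5 is another view of the extra variance in step 3, not an additional cost.

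**The case against.** The strongest reply is that randomization already deals with this. Gestational age at Baseline is fixed before allocation, so it is balanced in expectation, and the precision cost is small over most of the assumed range. Section 6.3 leaves room to adjust. The protocol also says openly that session numbers depend on timing. All of this stands, and it sets the size of the point. It does not remove it: section 6.3 names no variable and makes further adjustment conditional on observed imbalance, whereas the precision gain from a prognostic covariate is available with or without imbalance.

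There are stronger readings that a reader might infer, and the documents do not support them:

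- **That the arms are biased.** Nothing in the timing rules depends on the arm.
- **That gain before Baseline, being uncounted, dilutes the effect.** That weight precedes randomization and the intervention cannot change it, so leaving it out does not shrink the absolute difference between arms. A shorter intervention could reduce the effect in women who start late, but that is a disclosed feature of the design.
- **That slow clearance is the main cause.** No interval is reported. Spread in gestational age at recruitment contributes as well, and no delay is needed for it.
- **That eligibility must be capped at Baseline.** A cap would turn away consented women, leave the spread from recruitment timing in place, and add little once the covariate is in the model. Screening and clearance forms listed as attachments in section 13 are not in the supplied text, so an operational window there cannot be ruled out.

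**Conclusion.** The point holds as a matter of precision and pre-specification. Women contribute gain over windows of different length, and the plan does not commit to adjusting for it. The 0.5 to 1.6 kg figure describes one woman's measured gain, not an error in the comparison between arms. For the comparison, the cost is 0.04% to 9% extra variance, and at worst a fall from 80% to 76.5% power.

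These figures rest on assumed SDs and on even weekly gain. Even gain is a rough assumption: section 3.6.1 advises unchanged intake in the first trimester, so early weeks may count for less and later weeks for more. This is a free improvement, not a flaw that threatens Hypothesis 1.

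**What to change.** In section 6.3, state that the Hypothesis 1 model will include gestational age in weeks at the Baseline Visit as a covariate, whether or not the arms differ on it. Take it from the last-menstrual-period and ultrasound dating already used for eligibility.

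The cost is one line of text and one model term. It needs no new measurement beyond the date of the Baseline Visit, and no participants are lost. The covariate removes the part of the variance that is linear in start time; it does not equalize how long women receive the intervention, so the estimate remains an average over the start times actually enrolled.

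A limit on gestational age or on the interval to Baseline is optional and for the sponsor to judge; this point does not require one.

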### 3.6.8. Instrumentation:

- Contact information
- Demographics: Participants will complete a questionnaire regarding their age, parity, race, and ethnicity.
- Physical Assessment:
  - Weight: At all measurement visits, weight will be recorded in kilograms. Weight will be measured on a calibrated digital scale in duplicate, with the participant wearing light clothing and no shoes. While we will obtain the mother's weight at baseline, we will also obtain self-reported pregravid weight (before the last menstrual period). The difficulty of anticipating when a final weight should be obtained to capture the fullest extent of GWG was considered, and we elected to use an approach that afforded two possible weights that would be available for analytic purposes. The Week 36 weight will be the primary outcome except for mothers who deliver prior to 36 weeks, in which case we will use the Week 32 weight. Thus, we will have a final observation of GWG for all participants, regardless of whether they deliver earlier than 36 weeks.
  - Waist Circumference: As an indicator of subcutaneous and visceral abdominal fat, waist circumference will be measured (recorded in centimeters) using a non-distensible measuring tape and standard protocols for positioning.
  - Height: Height, using a wall-mounted stadiometer, will be recorded in centimeters. BMI will be calculated from measured weight and height.
- Physical Activity: We will assess physical activity, subjectively, using the International Physical Activity Questionnaire, as it has been used in other studies of gestational/postpartum weight management, has been validated against accelerometry, and has good test-retest reliability. We will also assess physical

activity objectively using the Actical accelerometer. Participants will be asked to wear the accelerometer for 7 days, including 2 weekend days and 3 weekdays.

- Weight Gain Recommendations: We will assess knowledge of weight gain recommendations at the Baseline visit, before randomization. One previous study has shown the gestational weight gain expectations, in a civilian population, predicted actual pregnancy weight gain; however, it is not certain whether this finding will replicate in a military population.
- Feeding Practices: Participants will be asked whether their child is being breastfed, partially breastfed (supplemented daily with formula or milk), or fully formula fed and whether solid foods are eaten daily. In addition, the duration of breastfeeding will be assessed. Breastfeeding status will also be used to calibrate postpartum calorie goals.
- Depression: Screening for depression at the first prenatal visit, 28 weeks gestation and at the 6-weeks postpartum visit is standard practice by the WHASC and SAMMC obstetric clinics using the Edinburgh Postnatal Depression Scale. We will obtain these scores from the participants' medical record. In addition, we will assess depression at the 6-weeks, 6-months and 12-months postpartum data collection visit, so we will be able to examine whether our results vary based on the presence of depression.
- Fitness Test Scores: We will obtain the final pregravid and the first postpartum fitness test score from active duty participants to be able to examine the impact of the interventions.
- Program Evaluation: Program satisfaction will be assessed to offer insight into program acceptability as well as barriers and facilitators to participation in each intervention arm. We will adapt the treatment satisfaction measure we are currently using in our "Fit Blue" study to evaluate acceptability and examine feedback on specific intervention aspects, which will inform program refinement and future implementation.
- Medical Outcomes and Health Care Utilization: Pregnancy-related medical outcomes will be obtained from the participant's medical record and will include: maternal (e.g., gestational diabetes, preeclampsia) and fetal conditions; type of delivery; Apgar score; gestational age at delivery; and birth weight and length of the infant. Length-for-age, weight-for-age and weight-for-length Z-scores will be calculated using the Center for Disease Control and Prevention (2000) reference data. Health care utilization (counts of ambulatory visits by type [physician, imaging, lab, other] and hospital/NICU admissions, hospital days) for mother and child will also be captured.

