### 3.6.2. Data Collection and Processing:

Measures will be obtained by trained staff who are blinded to treatment assignment. In-person follow-up data collection visits will be scheduled at gestational Week 32 and Week 36, as well as at 6-weeks, 6-months, and 12-months postpartum. If a study participant has moved out of the local area after enrolling in the study and continues to be a Tricare beneficiary, with the participant's permission, research staff will collect weight data via the participant's Body Trace scale uploads and other data instruments through the use of paper questionnaires mailed to the participant. In addition, telephone interventions will continue as normal per protocol. Relevant incentives (e.g., actual diapers given to participants) will be used to obtain high retention at all follow-up data collection visits. Incentives will not exceed the maximum amount specified by military policy. The diapers are an incentive and would be provided to a participant who attends the following data collection visits:

Year 1 (\$50 limit)	32 week visit	Choice of: \$15 worth of diapers, baby ointment, or wet bag
	36 week visit	Choice of: \$15 worth of diapers, baby ointment, or wet bag
	6 week post-partum visit	Handprint keepsake (\$10)
Year 2 (\$50 limit)	6 month post-partum visit	Choice of: \$15 worth of diapers, baby ointment, or wet bag
	12 month post-partum visit	Choice of: \$15 worth of diapers, baby ointment, or wet bag

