#### **6.3. Statistical Analysis:**

All of the analyses will be performed with SASv9.4. Data will be examined for distributional normality and outliers prior to any analyses. Descriptive statistics will be generated for all variables of interest included in the analysis, overall and by treatment arm. Univariate comparisons will consist of t-test, chi-square test, ANOVA, and their respective non-parametric counterparts if needed, for continuous/categorical variables respectively. Primary analyses will be intention-to-treat, without regard to intervention adherence. We will use multivariable linear ANCOVA-like regression models for continuous outcomes, to model and compare

the GWG (Hypothesis 1) and PPWL (Hypothesis 2), in the 3 arms. Using these models, treatment effects will be estimated and tested by comparing change in group-specific means at the final prenatal visit and 12-months postpartum conservatively adjusting for baseline differences (which will be minimal by virtue of randomization) and in the case of hypothesis 2 for 6-weeks postpartum weight differences. Randomization validity will be assessed by comparing arms on baseline measures using chi-square tests, ANOVAs and other appropriate tests. If imbalances are found, we will consider adjusting the between-group analyses for potential confounders.

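### The Week 32 fallback covers only delivery before 36 weeks, so gestational weight gain will not be observed for all participants, and no missing-data method is named for the women left out

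*Combined protocol and SAP*

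**What the plan says.** Section 3.6.8 (Instrumentation, Weight) makes the Week 36 weight the primary GWG outcome, "except for mothers who deliver prior to 36 weeks, in which case we will use the Week 32 weight". It then concludes: "Thus, we will have a final observation of GWG for all participants, regardless of whether they deliver earlier than 36 weeks". Section 6.1 restates the choice of visit as "either week 32 or week 36, depending on the delivery date". In both places the switch is governed by when the woman delivers, not by whether she attended.

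Section 6.3 says "Primary analyses will be intention-to-treat, without regard to intervention adherence" and "We will use multivariable linear ANCOVA-like regression models for continuous outcomes", with arms compared at the last prenatal visit for Hypothesis 1. It gives no method, assumption or sensitivity analysis for missing outcomes.

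Three other places bear on the point:

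- Section 3.6.2 plans for imperfect attendance: incentives "will be used to obtain high retention at all follow-up data collection visits". It accepts home-scale weights in one situation only: "If a study participant has moved out of the local area after enrolling in the study and continues to be a Tricare beneficiary", and with her permission.
- Section 3.6.7 sets early entry: "Participants must be less than 12 weeks gestation upon recruitment". The only miscarriage provision, in section 3.6.1, concerns loss before randomization.
- Section 3.6.5 counts 12 routine-care weights per participant, but no section makes them a source for the endpoint.

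**The concern.** The plan states a rule and draws from it a conclusion that the rule does not deliver. The gap that matters most is the woman still pregnant at 36 weeks who misses that visit. Her Week 32 weight has been measured under the study's own procedure, and the rule as written gives it no use in the first primary analysis.

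Two things are at stake. The first is precision. The second is bias in the arm contrast, if missed visits differ by arm and are related to gain. Differential attendance is plausible: before birth, two arms receive regular calls and weight feedback and the third receives no active intervention. Its direction is unknown. Because no rule is written down, the handling would be settled after the data are seen.

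**Working it through.** **Who has an endpoint under the written rule**

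| Situation after randomization | GWG endpoint under 3.6.8 and 6.1 |
|---|---|
| Attends Week 36 | Week 36 weight |
| Delivers in Weeks 32-36, attended Week 32 | Week 32 weight |
| Delivers in Weeks 32-36, missed Week 32 | None |
| Delivers before Week 32 | None |
| Still pregnant, has Week 32, misses Week 36 | None, although a weight exists |
| Pregnancy loss, or lost before Week 32 | None |

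A woman who has moved away may have a home-scale weight under section 3.6.2, so movers should not all be counted as missing. Rows three and four show that the conclusion fails even if it is read as a statement about early delivery only.

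**The plan's own figures.** Sections 6.2 and 6.4 give 755 enrolled, 450 completing and 150 per group: 450/3 = 150 and (755 − 450)/755 = 305/755 = 40.4% not completing. No power calculation can be reproduced, because alpha, power, effect size, SD and dropout rate are not stated. The 40.4% concerns the whole study to 12 months postpartum and may include losses before randomization. It is not used below as a Week 36 rate.

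**Assumed inputs.** 150 randomized per arm (450 in section 3.6.1); a share *m* = 10-20% missing Week 36 but having Week 32; Week 32 to Week 36 correlation *r* = 0.8-0.9; SD 4 kg (6 kg as an alternative); two-sided 5% test. Only the 150 comes from the documents.

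**Precision.** The variance relative to full data is 1/(1 − m) if these women are dropped, and r² + (1 − r²)/(1 − m) = 1 + (1 − r²)·m/(1 − m) if Week 32 informs Week 36. Effective n is 150 divided by the ratio.

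| m | Dropped: ratio, n | r = 0.8: ratio, n | r = 0.9: ratio, n |
|---|---|---|---|
| 10% | 1.11, 135 | 1.04, 144.2 | 1.02, 146.9 |
| 20% | 1.25, 120 | 1.09, 137.6 | 1.05, 143.2 |

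**Bias from dropping.** If missers gained *d* kg more than attenders in both arms, the contrast shifts by (difference in missing share) × *d*, in favour of the arm with more missing. The unadjusted standard error is SD × √(1/n₁ + 1/n₂). With b = shift/SE, the true error rate is P(Z > 1.96 − b) + P(Z < −1.96 − b).

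- 20% v 10%, d = 1-3 kg: shift = 0.10 × (1 to 3) = 0.1-0.3 kg. At SD 4, SE = 4 × √(1/120 + 1/135) = 0.502 kg, b = 0.20-0.60, error rate 5.5-9.2%.
- The same at SD 6: SE = 0.753 kg, b = 0.13-0.40, error rate 5.2-6.8%.
- 6% v 3%, d = 1-3 kg, SD 4: shift = 0.03 × (1 to 3) = 0.03-0.09 kg. SE = 4 × √(1/141 + 1/145.5) = 0.473 kg, b = 0.06-0.19, error rate 5.05-5.4%.
- Equal rates and equal selection: the shift is zero and only precision is lost.

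Covariate adjustment that lowers the SE would raise b.

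**What imputing from Week 32 recovers.** Simulated trials with no true effect, SD 4, r = 0.85 and about 20% v 10% missing:

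| Missingness driven by | Shift if dropped | Shift after imputation |
|---|---|---|
| Week 32 gain | −0.10 to −0.28 kg | about 0 |
| Week 36 weight itself | −0.41 kg | −0.15 kg |
| Gain unrelated to Week 32 | −0.20 kg | −0.21 kg |

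**The case against.** **Last visit attended.** Section 3.6.8 speaks of having two weights available for analysis. Sections 3.6 and 6.3 refer to the last pregnancy or prenatal visit. A reader might take this to mean the last visit attended, in which case Week 32 would be used. Neither section says so. That reading conflicts with 3.6.8 and 6.1, where delivery date decides, and it would count a 32-week gain as a 36-week gain. The objection stands this far: the text allows two primary datasets, and dropping these women is an inference about the default, since section 6.3 never specifies a complete-case analysis.

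**Other weights exist.** Routine clinic weights are counted in 3.6.5, and section 3.6.1 describes home scales that upload automatically. For some women these may fall nearer Week 36 than the Week 32 visit does. But no section makes either an endpoint source beyond the provision for movers. They are useful as auxiliary information; they do not close the gap in the rule.

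**Size.** Nothing in the documents supports 10-20% missing, or a 20% v 10% split. Visits take place in the obstetric clinics, with one visit and incentive schedule for everyone. This stands, and is why the 6% v 3% case is shown.

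**Over-enrolment.** Enrolling 755 to obtain 450 completers can restore precision. It cannot remove bias from differential missingness.

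**Conclusion.** The point holds as a should-fix. The statement that every participant will have a final GWG observation does not follow from the rule, and the plan gives no method for those without one. The consequence is modest. Under the assumed rates, up to 30 of 150 women per arm are dropped when most of their information could be kept. The bias is 0.1-0.3 kg (0.2-0.6 standard errors at SD 4 kg) under fairly unequal missingness, close to negligible at 6% v 3%, and zero if rates and selection are alike in the arms.

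Four stronger conclusions might be inferred, and the documents do not support them:

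- That 40% of women will lack a GWG endpoint. That figure is whole-study non-completion and at most an upper bound.
- That the error rate could be worked out on 755 randomized. The protocol's stated number randomized is 450.
- That the result will be biased, or biased in a known direction. Neither can be established from the text.
- That imputation removes the bias. It does so when missingness depends on Week 32 gain; otherwise some or all of the bias remains.

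The 12-month postpartum comparison also lacks a missing-data method. The sizes and the remedy here concern GWG only.

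**What to change.** 1. In section 3.6.8, qualify the claim that all participants will have a final observation. Have sections 3.6 and 6.3 refer to the endpoint as defined in 3.6.8 and 6.1.
2. Keep the observed Week 32 weight as the endpoint for women who deliver between Weeks 32 and 36. Gestational age at delivery, needed to identify them, is already collected.
3. For women still pregnant who miss Week 36, multiply impute the Week 36 weight from Week 32 weight, baseline weight, arm and screening BMI category (the randomization stratum), then fit the planned ANCOVA. Routine-care weights may be added as auxiliary variables where they are available in all arms. A standard repeated-measures model should not be offered as an equal option: it would implicitly predict Week 36 weights for early deliverers and so contradict item 2.
4. Do not impute after pregnancy loss. Report by arm the number of women with no GWG endpoint and the reason: pregnancy loss, delivery before Week 32, delivery in Weeks 32-36 with Week 32 missed, or lost earlier.
5. Add one sensitivity analysis that applies a delta shift to the unobserved Week 36 weights in continuing pregnancies.

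The cost is a few sentences and some programming, with no new visits or measurements. The drawback is that the primary result then rests on missing-at-random given these variables. The delta analysis can probe that assumption but cannot prove it. Women with no post-baseline weight will still add almost nothing.
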